**Official title: The efficacy of normobaric oxygen on chronic cerebral ischemia**

**NCT number: NCT03745092 (<http://www.clinicaltrials.gov>)**

**Date: December 1, 2018**

## **Study protocol**

### **Objective**

The aim of this study was to investigate whether the normobaric oxygen (NBO) could correct the chronic cerebral ischemia (CCI) induced EEG anomalies.

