### **Design and methods**

This was a prospective randomized cohort study and had been approved by the Institutional Ethic Committee of Xuanwu Hospital, Capital Medical University (Beijing, China) in accordance with the guidelines of the 1964 Declaration of Helsinki. Informed consent was obtained from all individuals before collecting any data. From December 2018 through December 2019, the patients who diagnosed as intracranial arterial stenosis or internal carotid arterial stenosis in Xuanwu Hospital, Capital Medical University and Beijing Fengtai You'anmen Hospital were enrolled in this study with random number table. The diagnosis of intracranial arterial stenosis and internal carotid arterial stenosis was confirmed by magnetic resonance angiography (MRA) and/or computed tomographic angiography (CTA). All of the enrolled subjects should comply with the following inclusion and exclusion criteria.

Inclusion criteria: (1) age from 18 to 80 years; (2) diagnosis of ICAS and/or ECAS; (3) NIHSS $\leq$ 4 and mRS $\leq$ 2; (4) signed informed consent.

Exclusion criteria: (1) brain infarction occurring within recent two months; (2) intracranial arterial aneurysm, dissection or malformation; (3) history of cerebral hemorrhage or subarachnoid hemorrhage; (4) history of cerebral trauma; (5) history of other brain injury or disorders; (6) austere diseases such as cancer, heart failure, respiratory failures; (7) respiratory diseases; (8) poor compliance.

The participants underwent 30-minute EEG recording two times. Between the two time recordings, they were randomly performed with NBO (received oxygen supplement with 8L/min, via Venturi mask, maintaining 45min) and rest (had a rest like lying, sitting or walking for 45min), which were labeled NBO group and control group in this study.

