The EEG recording was conducted with an EEG recording equipment (EEG YAL PN-NET, Beijing Yunshen Science and Technology Corporation). Ag/AgCl electrodes were positioned at Fp1, Fp2, F3, F4, F7, F8, Fz, C3, C4, Cz, P3, P4, Pz, T3, T4, T5, T6, O1, O2, A1, A2 (21 channels) according to the international 10-20 system, with electrode impedances all less than 5k $\Omega$ . The sampling rate was 256 Hz for all channels using a 16 bit AD convertor. Channel A1 and A2 were as references. Five minutes of artefact-free data was selected from EEG recordings in each subjects at random, and these participants should maintain awake and lying quietly with eyes closed as much as possible. Data filtering (band pass, 1 to 30Hz) was performed in EEGLAB (version 2019.1) with supplementary scripts operating in the MATLAB

environment. The artefact removal (blink artefact and electromyogram artefact) was performed again automatically using BSS algorithm (sobi) that was implemented into EEGLAB software packages.

The absolute power (AP, with units  $\mu\text{V}^2$ ) was computed using Fast Fourier Transform (FFT) for each electrode over the delta (1-4 Hz), theta (4-8 Hz), alpha (8-13 Hz) and beta (13-20 Hz) frequency bands, and the relative power (RP) was a ratio of the frequency band of interest power to the total power across the 1-20Hz range. The power spectral density (PSD) for each channels was estimated via Welch's procedure with a 2-s Hamming window length. Besides over all channels, fronto-central electrodes (F3, F4, Fz, C3, C4, Cz) which were with mild occipital alpha oscillation impact, were also used to reflect the actual frequency activities in the forehead. Proceeded by python software, the EEG wavelet entropy was calculated via nonlinear dynamics method in order to evaluate the complex of brain function. Power ratio index (PRI) was defined as AP ratios of theta/alpha (TAR), delta/alpha (DAR), (delta+theta)/(alpha+beta) (DTABR), and fronto-central alpha/occipital alpha (FOAR) in this study. Each frequency band AP and RP reduction rate was calculated as a ratio of pre-intervention minus post-intervention bandpower to pre-intervention bandpower.

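### The objective claims correction of ischemia-induced EEG anomalies, but the design defines no anomaly and no favourable direction, so it can show only an EEG change against rest

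*Combined protocol and SAP*

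**What the plan says.** All references are to the combined protocol and SAP.

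- **Objective.** The aim is to learn whether NBO "could correct the chronic cerebral ischemia (CCI) induced EEG anomalies". No anomaly or target value is named.
- **Design and methods, eligibility.** The disease criterion is "diagnosis of ICAS and/or ECAS"; the diagnosis "was confirmed by magnetic resonance angiography (MRA) and/or computed tomographic angiography (CTA"). The other inclusion criteria are age, NIHSS of at most 4 with mRS of at most 2, and consent. No degree of stenosis is stated, and neither EEG nor perfusion appears among the 4 inclusion and 8 exclusion criteria.
- **Design and methods, arms.** Patients receive 45 minutes of oxygen or 45 minutes of rest between two EEG recordings, "which were labeled NBO group and control group in this study". There is no non-ischemic group and no normative data.
- **Design and methods, EEG measures.** The plan lists absolute power (AP) and relative power (RP) in four bands, over all channels and over fronto-central electrodes. It adds four power ratios (TAR, DAR, DTABR, FOAR) and wavelet entropy. "Each frequency band AP and RP reduction rate was calculated" as (pre minus post)/pre, with the same formula for every band. No primary measure, normal range or favourable direction is given.
- **Statistical analysis.** Between-group tests, within-group pre/post tests and a linear regression with unnamed covariates are allowed, each judged at p<0.05. No success criterion is stated.

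**The concern.** The objective presupposes three things: that an EEG anomaly is present, that ischemia caused it, and that a known direction of change counts as correcting it. The design supplies none of them.

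A patient with stenosis and an entirely normal EEG is eligible, and in that patient there is nothing to correct. An effect of oxygen or the mask that would appear equally in people without ischemia cannot be told apart from an effect on ischemic brain. Without a stated direction, a fall or a rise in a given measure could each be presented as favourable once the result is known.

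What is at stake is the conclusion, not the usability of the data. A plan followed exactly could end in a statement about correcting ischemic EEG abnormality that does not follow from the comparison made.

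**Working it through.** The plan gives no sample size, power, effect size or SD, so there is no design figure to reproduce. The check is a comparison of the objective with the design, followed by two short calculations.

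**1. What the objective needs and what the plan provides**

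| Needed | Provided |
|---|---|
| An abnormal EEG, or a definition of one | No entry criterion, threshold, normal range or reference group |
| Evidence that ischemia is the cause | Vessel imaging only; exclusion of other brain disease and adjustment for unnamed covariates |
| A direction that counts as correction | None for any band, ratio or entropy |

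**2. Can the reduction rate stand in for a direction?** RP is band power divided by total 1–20 Hz power, and the four bands (1–4, 4–8, 8–13, 13–20 Hz) fill that range. The four RPs therefore sum to 1 before and after. With rate r = (pre − post)/pre for each band,

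Σ pre × r = Σ pre − Σ post = 1 − 1 = 0.

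Hypothetical example in the order delta, theta, alpha, beta:

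- pre: 0.30, 0.20, 0.35, 0.15
- post: 0.25, 0.18, 0.40, 0.17
- rates: 0.167, 0.100, −0.143, −0.133
- weighted sum: 0.05 + 0.02 − 0.05 − 0.02 = 0

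A fall in one band's RP forces a rise in at least one other. Reduction cannot be favourable in all four bands, and the plan does not say in which it is. A directed ratio avoids this: in the same example DTABR goes from 0.50/0.50 = 1.00 to 0.43/0.57 = 0.75, a single change whose meaning could be fixed beforehand.

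**3. How much room the open definition leaves.** One possible count of listed measures is (4 AP + 4 RP) × 2 regions = 16, plus 4 ratios and 1 entropy = 21, leaving out the reduction rates. With no true effect and k independent tests at 0.05, the chance of at least one p<0.05 is 1 − 0.95^k.

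| k | Chance |
|---|---|
| 3 | 14.3% |
| 5 | 22.6% |
| 8 | 33.7% |
| 13 | 48.7% |
| 21 | 65.9% |

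The measures are correlated, so 65.9% is the independence figure. The rows for 3 to 13 show a range of assumed effective numbers of tests. Testing each of the 21 both between arms and within the NBO arm (42 tests) gives 88.4% under independence.

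Fixing a direction halves the per-test chance of a false favourable result to 0.025 (two-sided tests assumed; the plan does not state sidedness). For 21 directed, independent tests it is 1 − 0.975^21 = 41.2%; for one directed main measure it is 2.5%. Direction alone is therefore not enough, and a main measure is needed as well.

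**The case against.** The strongest reply is that the randomised rest arm and the p<0.05 threshold already discipline the claim. This stands in part. The between-arm contrast is a sound basis for saying that NBO changes the EEG relative to rest, and a reader who infers that any EEG shift at all could be called success goes further than the documents allow. The shift must be nominally significant. It may, however, be in any listed measure and in either direction.

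Three other strong readings also fail.

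- A reader might infer that, if NBO shifts the EEG whether or not ischemia is present, the stated conclusion must be false whenever a test is significant. That does not follow: a treatment that acts on everyone can still correct an abnormality in those who have one. The design leaves the claim unsupported; it does not make it false.
- A reader might take the reduction rate as the sole outcome. It is one of several, and it is signed, so opposite changes remain distinguishable. What is missing is the statement of which sign is favourable.
- A reader might expect a larger NBO effect in patients with more baseline slowing to prove correction of ischemic change. It would not. Slowing may reflect age (18 to 80 years) or drowsiness, and an effect proportional to baseline produces the same pattern.

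There is also real mitigation. The exclusions, including "5) history of other brain injury or disorders", remove several rival causes, and the EEG segments are meant to be awake with eyes closed. TAR, DAR and DTABR all put slow power over faster power, which hints that slowing is the anomaly in mind. None of this establishes an ischemic cause, and the text never turns the hint into a stated direction.

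Finally, part of the calculation overlaps with the lack of a primary endpoint and of multiplicity control. The point particular to this item is that the objective's wording outruns the design and that direction is unstated.

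**Conclusion.** The concern holds as a mismatch between objective and design. The plan can answer whether NBO changes EEG measures compared with rest in patients with intracranial or carotid stenosis. It cannot answer whether an ischemia-induced anomaly was corrected, and it leaves a nominally significant change of either sign in any listed measure open to that description.

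The textual part needs no assumption: the reference, threshold and direction are absent. The numerical part, 14% to 49% for 3 to 13 effective tests and 65.9% for 21 independent ones, rests on one way of counting measures and on assumed correlation. It indicates scale and is not an estimate of this trial's error rate. The randomised data remain usable, so this should be changed but does not undermine the trial.

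**What to change.** 1. Restate the objective and the permitted conclusion as whether one 45-min NBO session changes quantitative EEG measures compared with rest in patients with intracranial or carotid stenosis.
2. Name one main measure for the between-arm comparison, for example DTABR with lower as favourable, and say which electrode set it uses. State that a change the other way is not improvement.
3. Treat measures without a stated direction (FOAR, wavelet entropy, AP and RP of individual bands) as descriptive.
4. If an arm-by-baseline interaction is fitted in the planned regression, label it exploratory. It should not decide whether the claim is made.

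The main measure and its direction should be recorded before any EEG results are seen by arm. The cost is rewording and a narrower claim; no additional patients, recordings or reference group are needed. Keeping the word correction in the objective would instead require defining the anomaly against a reference group or norms, which is a larger change, and evidence that ischemia is its cause.

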### **Design and methods**

This was a prospective randomized cohort study and had been approved by the Institutional Ethic Committee of Xuanwu Hospital, Capital Medical University (Beijing, China) in accordance with the guidelines of the 1964 Declaration of Helsinki. Informed consent was obtained from all individuals before collecting any data. From December 2018 through December 2019, the patients who diagnosed as intracranial arterial stenosis or internal carotid arterial stenosis in Xuanwu Hospital, Capital Medical University and Beijing Fengtai You'anmen Hospital were enrolled in this study with random number table. The diagnosis of intracranial arterial stenosis and internal carotid arterial stenosis was confirmed by magnetic resonance angiography (MRA) and/or computed tomographic angiography (CTA). All of the enrolled subjects should comply with the following inclusion and exclusion criteria.

Inclusion criteria: (1) age from 18 to 80 years; (2) diagnosis of ICAS and/or ECAS; (3) NIHSS $\leq$ 4 and mRS $\leq$ 2; (4) signed informed consent.

Exclusion criteria: (1) brain infarction occurring within recent two months; (2) intracranial arterial aneurysm, dissection or malformation; (3) history of cerebral hemorrhage or subarachnoid hemorrhage; (4) history of cerebral trauma; (5) history of other brain injury or disorders; (6) austere diseases such as cancer, heart failure, respiratory failures; (7) respiratory diseases; (8) poor compliance.

The participants underwent 30-minute EEG recording two times. Between the two time recordings, they were randomly performed with NBO (received oxygen supplement with 8L/min, via Venturi mask, maintaining 45min) and rest (had a rest like lying, sitting or walking for 45min), which were labeled NBO group and control group in this study.

The EEG recording was conducted with an EEG recording equipment (EEG YAL PN-NET, Beijing Yunshen Science and Technology Corporation). Ag/AgCl electrodes were positioned at Fp1, Fp2, F3, F4, F7, F8, Fz, C3, C4, Cz, P3, P4, Pz, T3, T4, T5, T6, O1, O2, A1, A2 (21 channels) according to the international 10-20 system, with electrode impedances all less than 5k $\Omega$ . The sampling rate was 256 Hz for all channels using a 16 bit AD convertor. Channel A1 and A2 were as references. Five minutes of artefact-free data was selected from EEG recordings in each subjects at random, and these participants should maintain awake and lying quietly with eyes closed as much as possible. Data filtering (band pass, 1 to 30Hz) was performed in EEGLAB (version 2019.1) with supplementary scripts operating in the MATLAB

environment. The artefact removal (blink artefact and electromyogram artefact) was performed again automatically using BSS algorithm (sobi) that was implemented into EEGLAB software packages.

The absolute power (AP, with units  $\mu\text{V}^2$ ) was computed using Fast Fourier Transform (FFT) for each electrode over the delta (1-4 Hz), theta (4-8 Hz), alpha (8-13 Hz) and beta (13-20 Hz) frequency bands, and the relative power (RP) was a ratio of the frequency band of interest power to the total power across the 1-20Hz range. The power spectral density (PSD) for each channels was estimated via Welch's procedure with a 2-s Hamming window length. Besides over all channels, fronto-central electrodes (F3, F4, Fz, C3, C4, Cz) which were with mild occipital alpha oscillation impact, were also used to reflect the actual frequency activities in the forehead. Proceeded by python software, the EEG wavelet entropy was calculated via nonlinear dynamics method in order to evaluate the complex of brain function. Power ratio index (PRI) was defined as AP ratios of theta/alpha (TAR), delta/alpha (DAR), (delta+theta)/(alpha+beta) (DTABR), and fronto-central alpha/occipital alpha (FOAR) in this study. Each frequency band AP and RP reduction rate was calculated as a ratio of pre-intervention minus post-intervention bandpower to pre-intervention bandpower.

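### The 45 minutes between the two EEGs are not the same in both arms: controls may lie, sit or walk, oxygen patients have no stated activity, and no mask or air control is described

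*Combined protocol and SAP*

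**What the plan says.** All of the following is in the combined protocol and SAP.

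- **Aim (Objective).** The question is "whether the normobaric oxygen (NBO) could correct the chronic cerebral ischemia (CCI) induced EEG anomalies".
- **Timing (Design and methods).** "The participants underwent 30-minute EEG recording two times", with the assigned condition in between.
- **Oxygen arm (Design and methods).** Patients "received oxygen supplement with 8L/min, via Venturi mask, maintaining 45min". No posture, activity or wakefulness is given.
- **Control arm (Design and methods).** "rest (had a rest like lying, sitting or walking for 45min), which were labeled NBO group and control group in this study".
- **State for the EEG data (Design and methods, EEG paragraphs).** "these participants should maintain awake and lying quietly with eyes closed as much as possible".
- **Data analysed (same paragraphs).** "Five minutes of artefact-free data was selected from EEG recordings in each subjects at random".
- **Outcome (same paragraphs).** "Each frequency band AP and RP reduction rate was calculated as a ratio of pre-intervention minus post-intervention bandpower to pre-intervention bandpower".
- **Analysis (Statistical analysis).** A linear regression is planned to deal with other covariates, but none is named.

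No section describes a settling period before the second EEG, a record of what patients did in the interval, a sham mask, an air-flow control, or blinding.

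**The concern.** The oxygen arm and the control arm may differ in more than oxygen. A control patient may walk for 45 minutes or lie down for 45 minutes; what an oxygen patient does while wearing the mask is not stated. Randomisation balances the patients at baseline. It does not balance what happens afterwards, and here the conduct of the interval is part of how the arms are defined.

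If arousal or activity persists into the second recording, it goes straight into the outcome, because the reduction rate compares the post-intervention value with the pre-intervention value. The objective attributes EEG correction to oxygen, so a positive result could be partly an activity effect, and a null result could be partly an activity effect in the opposite direction. The documents do not show which way it would go.

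The missing mask or air control is a second, independent point. It needs no carry-over of activity. Without such a control, an arm difference cannot be assigned to oxygen rather than to wearing a mask, feeling gas flow, or expecting benefit.

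**Working it through.** The plan gives no sample size, effect size or SD, so there is no figure of its own to reproduce. The check has two parts.

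**1. Does anything in the plan make the interval comparable?**

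- Randomisation: no, because the activity occurs after assignment.
- The awake, supine, eyes-closed request: it applies to both arms and helps, but it governs the EEG data, not the preceding 45 minutes, and only as far as achievable.
- Random choice of five minutes: it dilutes a short after-effect but not a lasting one.
- Regression: no covariate is named and no activity record is described. Adjusting for behaviour after randomisation would not restore a clean comparison in any case.

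**2. How large could the activity bias be?** Only the selection of 5 minutes at random from 30 comes from the documents. Everything else below is assumed.

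Let *d* be the bias from activity alone, in SDs of the change score:

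*d* = (difference between arms in proportion active) × (shift per active patient, in SD) × *f*

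Here *f* is the mean share of the analysed five minutes that falls within the first *L* minutes of the second EEG. The gap between the 45 minutes and that EEG is not given and is taken as zero; a longer gap lowers *f*.

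- One continuous block, start uniform on 0–25 min: *f* = (*L* − 2.5)/25 for *L* from 5 to 25. *L* = 5 gives 0.10, *L* = 10 gives 0.30, *L* = 20 gives 0.70. *L* = 30 gives 1.
- Scattered epochs: *f* = *L*/30, so *L* = 10 gives 0.33.

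The rejection probability is that of a two-sided two-sample t test at 0.05, with df = 2*n* − 2 and noncentrality *d*/√(2/*n*), *n* per arm.

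False-positive rate with no oxygen effect and a shift of 0.2 SD:

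| Difference in proportion active | Carry-over *L* | *d* | *n* = 20 | *n* = 50 | *n* = 100 |
|---|---|---|---|---|---|
| any | none | 0 | 5.0% | 5.0% | 5.0% |
| 0.25 | 10 min | 0.25 × 0.2 × 0.30 = 0.015 | 5.0% | 5.1% | 5.1% |
| 0.25 | 30 min | 0.25 × 0.2 × 1 = 0.05 | 5.3% | 5.7% | 6.4% |
| 0.5 | 10 min | 0.5 × 0.2 × 0.30 = 0.03 | 5.1% | 5.3% | 5.5% |
| 0.5 | 30 min | 0.5 × 0.2 × 1 = 0.10 | 6.1% | 7.9% | 10.8% |

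A simulation with half of controls and no oxygen patients active (100,000 trials per cell) agreed within about 0.001.

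Shift needed to double the 5% to 10%. The required *d* is 0.212 / 0.132 / 0.093 for *n* = 20 / 50 / 100. At a difference of 0.5 in proportion active:

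- 30-minute carry-over (divide by 0.5): 0.42 / 0.26 / 0.19 SD.
- 10-minute carry-over (divide by 0.5 × 0.30 = 0.15): 1.41 / 0.88 / 0.62 SD.

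Power with an assumed true effect of 0.5 SD and a bias in the opposite direction:

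| Opposing *d* | *n* = 20 | *n* = 50 | *n* = 100 |
|---|---|---|---|
| 0 | 34% | 70% | 94% |
| 0.03 | 30% | 64% | 91% |
| 0.10 | 23% | 51% | 80% |

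Mask and expectation effects are not in *d*, and the documents offer nothing from which to size them.

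**The case against.** The strongest reply is that the bias needs three links, none of which the documents supply: that the arms actually differed in activity, that activity shifts band power, and that the shift lasts into the five minutes analysed. Silence about posture in the oxygen arm is not evidence of a difference; those patients may also have lain or sat. This stands, and it is why the point is conditional.

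The size of the illustration is also open to challenge. A difference of 0.5 in proportion active has no source, and halving it to 0.25 takes the 30-minute false-positive rate at 100 per arm from 10.8% to 6.4%. The analysed data must be free of artefact, so restless early minutes may be picked less often than the formula for *f* assumes. The plan's outcome is a ratio, with a Mann-Whitney test where data are not Gaussian, so a t test on change scores is only an approximation. These points stand too. They bear on the illustration, not on the fact that the interval is left open.

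Finally, the text is in the past tense, so changing the procedure may no longer be possible. That limits the remedy to reporting and wording for patients already studied; it does not remove the limitation.

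None of this answers the separate point about the missing mask or air control.

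**Conclusion.** The concern holds. As written, the trial compares a mask oxygen session with unstandardised rest, not oxygen with no oxygen under otherwise equal conditions. Nothing in the plan standardises or records the 45 minutes, and randomisation cannot balance them.

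The documents do not show that a bias occurred, nor its direction. Under the assumptions above, the activity bias is negligible if carry-over is short or small: about 5.0% to 5.5% false positives for 10-minute carry-over with a 0.2 SD shift. It becomes material if carry-over lasts through the recording: up to 10.8% false positives, or a loss of power from 94% to 80%, at 100 per arm with *d* = 0.10. Those figures rest on assumed sample sizes, proportions active, shift, carry-over length and true effect.

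The point should be addressed because the difference between arms is avoidable at little cost, not because a bias has been demonstrated. Confidence is medium. The attribution problem from the absent mask or air control applies whether or not activity carries over.

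**What to change.** **Procedure.** Replace the open choice of control activity with one posture, activity and wakefulness instruction, applied identically to both arms for the 45 minutes. Record compliance in both arms.

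**Conclusion.** Word it as a mask oxygen session versus rest. A common instruction does not solve the mask and expectation problem, so without a mask or air control the claim should not be about oxygen alone.

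**Patients already studied.** Report what each arm did in the interval where this is known. Compare all randomised patients by assigned arm. Treat any analysis by activity as supportive only, because it selects on behaviour after randomisation. Limit the conclusion to a mask oxygen session versus unstandardised rest.

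**Cost.** One sentence in the procedure and one more item on the record. Controls lose the freedom to move for 45 minutes, and the conclusion is narrower. For patients already studied, only the reporting and the wording can change.

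### The comparison is open, and the plan describes no masking of whoever judges which EEG stretches are artefact-free; the random draw protects only the choice made after that judgement.

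*Combined protocol and SAP*

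**What the plan says.** All of the following is in the combined protocol and SAP, Design and methods.

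- **Arms.** Between two recordings, patients "they were randomly performed with NBO (received oxygen supplement with 8L/min, via Venturi mask, maintaining 45min" or had "rest (had a rest like lying, sitting or walking for 45min), which were labeled NBO group and control group in this study". No sham mask or sham gas is described for the control arm.
- **Recordings.** "The participants underwent 30-minute EEG recording two times", once before and once after the 45-minute period.
- **Extract analysed.** "Five minutes of artefact-free data was selected from EEG recordings in each subjects at random". Patients were to be awake and still with their eyes shut, as far as possible.
- **Later cleaning.** After band-pass filtering, removal of blink and muscle artefact "was performed again automatically using BSS algorithm (sobi) that was implemented into EEGLAB software packages".
- **Outcomes.** Band powers, power ratios and wavelet entropy are computed from the processed EEG. Change is expressed so that "Each frequency band AP and RP reduction rate was calculated as a ratio of pre-intervention minus post-intervention bandpower to pre-intervention bandpower".

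Neither this section nor Statistical analysis mentions masking of the patient, the technician, the person who selects segments or the analyst. The plan does not say what makes a stretch artefact-free, who decides it, or how the random selection is carried out.

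**The concern.** Taking five minutes from thirty involves two steps. Some stretches are accepted as usable, and then five minutes are drawn from them. The words on randomness cover the second step. The first comes earlier and decides what can be drawn at all.

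In an open comparison, a person who knows that a file is a post-oxygen recording might, without intending to, discard slow or drowsy-looking stretches more readily there than in a control file. Slow activity is measured directly (delta and theta power and the ratios built on them), so unequal rejection could appear as a treatment difference.

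The analysis cannot undo this. The t tests, rank tests and regression in Statistical analysis take the band-power and entropy values as given. Randomisation balances patients at allocation; it does not protect against unequal handling of their recordings afterwards.

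**Working it through.** **Reading the steps in order**

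1. The difference between the arms is visible: a mask with oxygen against rest, with no sham described.
2. A random draw needs a pool to draw from, and here the pool is the artefact-free part of the recording. Acceptance therefore comes before the draw.
3. The automatic cleaning is described as done again, after selection and filtering. The text does not say whether the first screen was manual or automatic.
4. No sentence hides arm or recording order at any of these steps.

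**Size: an illustration**

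The plan states no sample size, SD or effect size, so it has no figure to reproduce.

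Inputs:
- Candidates per recording: 30 min / 5 min = 6 non-overlapping segments. The two durations are from Design and methods; treating the segments as separate candidates is an assumption.
- Segment values within a recording are taken as independent and normal (assumption).
- Within-person segment SD = 0.3 of the between-person SD (assumption).
- The m least favourable of the six are rejected, and one of the rest is drawn with equal chance. This is done in a fraction f of NBO post-files and in no other files (assumption).

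The expected values of six ordered standard normals are ±1.267, ±0.642 and ±0.202. All six sum to zero, so the values left after rejecting the m lowest sum to the absolute total of those rejected. Hence

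shift = f × 0.3 × (absolute sum of the m lowest) / (6 − m).

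| Rejected (m) | Mean of the rest, in segment SDs | f = 1, in between-person SDs | f = 0.25 |
|---|---|---|---|
| 1 | 1.267 / 5 = 0.253 | 0.253 × 0.3 = 0.08 | 0.02 |
| 2 | 1.909 / 4 = 0.477 | 0.477 × 0.3 = 0.14 | 0.04 |
| 3 | 2.111 / 3 = 0.704 | 0.704 × 0.3 = 0.21 | 0.05 |

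The result is proportional to the assumed SD ratio. With the ratio halved to 0.15, the f = 1 column becomes 0.04, 0.07 and 0.11. With it doubled to 0.6, it becomes 0.15, 0.29 and 0.42.

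**If acceptance is unbiased**

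In a simulation with no true effect, 20, 30 or 50 patients per arm (assumed) and segments drawn truly at random in both arms, the arm difference averaged about zero. A two-sided t test at 0.05 was significant in 4.7% to 5.2% of runs. So the random draw does its job when the pool it draws from is not itself distorted.

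**The case against.** The strongest reply is that the plan says the selection is random, and a genuine random draw prevents anyone from picking a convenient segment. That is correct, and it rules out the more dramatic reading. A reader might infer that a handler could choose the best of several acceptable segments. Under the same assumptions, that would shift the mean by 0.564 × 0.3 = 0.17 SD for the better of two, or 1.268 × 0.3 = 0.38 SD for the best of six. Those figures describe the very choice that a random draw excludes. To reach 0.38 SD through acceptance alone, five of the six segments would have to be rejected in every NBO post-file, and nothing in the text suggests that.

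Four further replies also stand:

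- **Silence is not proof.** The plan does not say that selection was unmasked or manual, or that the person selecting knew the arm. These are possibilities left open.
- **Excluding drowsy stretches can be legitimate.** The plan asks for quiet wakefulness with eyes closed. Only exclusion that differs by arm or by recording is bias.
- **The direction is not uniform.** The four bands together make up the 1–20 Hz total used for relative power, so if one share falls, at least one other must rise. A reader might infer that every measure moves in favour of oxygen; the documents do not support that.
- **The scale is only one of those reported.** The illustration uses between-person SDs, while the plan also reports a proportional pre-to-post reduction.

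None of this supplies masking or criteria for the acceptance step.

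**Conclusion.** The point holds in a limited form. The comparison is open, and the plan describes no masking to arm or to pre/post of the judgement that decides which EEG minutes are eligible. It states no criteria for that judgement and no mechanism for the random draw. Bias in the between-arm contrast therefore cannot be excluded. The documents do not show that it occurred, and they do not support saying that the EEG stage has no protection.

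The illustrated size is about 0.08 to 0.21 between-person SD if one to three of six segments are wrongly rejected in every NBO post-file, and about 0.02 to 0.05 SD if in a quarter of them. This rests on the assumed SD ratio of 0.3, on normal independent segments and on rejection in one arm's post-files only. It indicates a possible scale and is not an estimate for this trial.

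This is a cheap improvement to conduct. Masking patients to a mask-versus-rest comparison is hard; masking the reader of a stored digital file is not.

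**What to change.** Amend the EEG paragraphs of Design and methods so that:

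1. before anyone reviews a recording, all EEG files are exported under a random code that hides both arm and recording order;
2. the artefact and wakefulness criteria are written down in advance and applied to coded files only;
3. the five minutes are drawn from the eligible stretches by a documented program with a recorded seed;
4. the code is broken only after the band-power and entropy values are locked.

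If segments were already chosen without masking, repeat the selection on coded files.

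Cost: a renaming script, a sealed key and a short written rule. No extra reader, procedure or patient visit is needed. The drawback is a short delay before results by arm can be seen, or some rework if segments have already been chosen.
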